2.4.1 Risks of IVIG

Like the FLU-IVIG Pilot, the IVIG used in this study will be manufactured in the same manner and to the same standards as commercially available (non-influenza antibody enriched) IVIG. This includes screening for blood-borne pathogens and manufacturing steps that include solvents/detergents to inactivate any viruses. There are no anticipated unique risks to an anti-influenza antibody enriched IVIG; therefore the risks are anticipated to be the risks of standard IVIG preparations. Common risks include fever, rash, hives, or headache. Other more serious risks are rare and include serious allergic reactions including anaphylaxis, hemolysis, and aseptic meningitis. As IVIG is made from human plasma, transmittable viral infections such as hepatitis B, hepatitis C, and human immunodeficiency virus (HIV) are a potential risk, although steps are taken to screen for and inactivate such pathogens. In addition, there is a theoretical risk, although low, that IVIG administration may be capable of transmitting other known or unknown infectious agents other than viruses, such as infectious prions (e.g., the agent of Creutzfeldt-Jakob disease).

Immune globulin administration may impair the efficacy of live attenuated virus vaccines such as measles, rubella, mumps and varicella. Renal dysfunction, acute renal failure, and osmotic nephropathy may occur with immune globulin intravenous products in predisposed patients. Renal dysfunction and acute failure occur more

commonly in patients receiving IVIG products containing sucrose. The influenza IVIG preparation used in this study does not contain sucrose.

Although rare, transfusion-related acute lung injury (TRALI) may occur with IVIG therapy and is characterized by severe respiratory distress, pulmonary edema, hypoxemia, normal left ventricular function, and fever.

There are case reports of pulmonary emboli occurring after administration of IVIG and plasma therapy, although definitive studies assessing risk are lacking.³² In one series 5 of 10 patients critically ill with A(H1N1)pdm09 were shown to have pulmonary emboli.³³ This high percentage has not been shown in other H1N1 series, and pulmonary emboli have been shown to develop in approximately 10-15% of critically ill adults.³⁴ However, the potential risk of pulmonary embolism exists. Other thrombotic events, including myocardial infarction, cerebral vascular accident, and deep vein thrombosis may also occur.

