4.2.5 Reporting of Adverse Events

INSIGHT 006: FLU-IVIG

As noted in section 2.4.1 there are potential risks associated with taking IVIG. These risks include fever, rash, hives, headache, allergic reactions, transmitted infections, renal dysfunction/failure, TRALI and pulmonary embolism. The risk of transmitted infections is considered low because of the screening of the plasma used to make the IVIG.

Some of these risks are similar to symptoms associated with influenza. Also, it is expected that many participants will have co-morbid conditions that are associated with signs, symptoms and laboratory abnormalities that are similar to possible risks of IVIG. Thus, AEs will be collected irrespective of perceived relationship to treatment in order to compare differences between the IVIG and placebo groups.

Through 28 days of follow-up, AE data collection will be restricted to any new grade 3 or 4 AE, or previously existing AEs which have increased in severity to grade 3 or 4.

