The following clinical secondary outcomes are of interest: 1) percent alive and out of the hospital at Day 14; 2) change in NEW score at Day 3; and 3) resumption of normal activities at Day 14. It is expected that IVIG will have a favorable effect on each of these outcomes as well as the ordinal primary outcome. Since the primary endpoint and these secondary endpoints are related and expected to be correlated, before examining each secondary endpoint separately, a single global test will be carried out using the method described by O'Brien and Pocock. ^{45,46} With this approach, the endpoints will be equally weighted and a single global test statistic will be determined. This single global test is expected to have greater power than the test for each endpoint separately. For example, for a common correlation among the four outcomes of 0.50, the average Z value must be 1.55 (instead of 1.96) to achieve a significance level of 0.05. The combined evidence using all four outcomes does not have to be as extreme as for a single outcome.

Time to death and time to hospital discharge will be summarized with Kaplan-Meier plots and Cox models. For time-to-event analyses, time will be measured from randomization. The comparison of NEW scores and HAI titers will be compared using analysis of covariance with the baseline score or titer as a covariate. HAI titer levels will be log-transformed and the data at each time point will be summarized as the ratio of geometric means for those assigned IVIG and placebo.

Longitudinal random effects models will also be used to summarize repeated assessments of the ordinal outcome, HAI titers and the NEW score. By collecting specific dates when patients are removed from the ICU and oxygen, discharged and resume normal activities, the ordinal outcome can be defined for a patient on each day of follow-up.

Symptoms reported and AEs will be compared for the IVIG and placebo groups and summarized using chi-square statistics. Laboratory measurements will be summarized as changes from baseline to Day 7.

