Appendix B: Time and Events Schedule

Screening and Baseline			
	Day -2 to 0	Day 0	
ELIGIBILITY AND SCREENING			
Informed consent	X		
Demographics, medical history	Х		
Influenza testing	Х		
Pregnancy test, if child-bearing potential	Х		
CBC, Chemistry panel, PTT/PT/INR ^a	Х		
NEW score	X		
DAY OF RANDOMIZATION			
Assessment of targeted symptoms		X	
NEW score ^b		X	
Randomize participant		Х	
Serum & plasma for storage & serology ^c		Х	
NP swab for virus isolation		X	
IVIG/placebo infusion		X	

	Day 1	Day 2 ^d	Day 3	Day 7 +1 day	Day 14 ^d ±2 days	Day 28 ^d +7 days
STUDY PROCEDURES						
NEW score ^e	Х	Х	Х			
Assessment of targeted symptoms ^f			Х	Х		
Clinical data	Х	Х	Х	Х	Х	Х
Adverse events	Х	Х	Х	Х	Х	Х
LOCAL LAB						
CBC, Chemistry panel ^a				Х		
CENTRAL LAB						
NP swab for virus isolation			Х			
Serum & plasma for storage and serology ^c	Х		Х	Х		

^a CBC includes white cell count with differential (neutrophil, lymphocyte, eosinophil percentages), hemoglobin, hematocrit, and platelets. Chemistry panel includes sodium, potassium, serum bicarbonate, BUN, creatinine, glucose, albumin, ALT/GPT, AST/GOT, total bilirubin.

^b NEW score must be repeated on day 0 if the score used for screening was from a previous day. The NEW score at screening must be ≥ 2.

^c Sufficient for 4 1-mL aliquots of serum and 4 1-mL aliquots of plasma

d May be assessed via telephone, if not hospitalized.

^e Assessed twice daily, at 8:00 AM and 4:00 PM (±2 hours), while hospitalized.

FParticipants are given a diary at hospital discharge to use for this assessment, and for recording resolution of flu symptoms and return to normal activities.

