The IVIG and placebo group will also be compared for the percentage with undetectable viral RNA at day 3 using logistic regression with baseline viral load as a covariate and geographic region and influenza subtype as stratifying factors. For this analysis, exclusions will be as per the previous paragraph; however, participants dying on or before day 3 (currently one participant) will be included in these analyses and considered as having detectable RNA.

Ordinal outcomes will be summarized using a proportional odds model as described for the primary ordinal outcome (see E.).

Binary outcomes will be summarized with logistic models that are stratified by geographic region and include indicators for the participant's clinical status at entry (ICU, general ward on supplemental oxygen, general ward not on supplemental oxygen), and an indicator for whether the participant was in the IVIG pilot trial (FLU 005) or the FLU-IVIG trial (FLU 006).

Reference viruses used for HAI titers changed over the course of the study corresponding to the circulating viruses. Longitudinal random effects models stratified by subtype (H1N1, H3N2, B) will be used to estimate differences in log-transformed HAI titers between the IVIG and placebo group at days 1, 3 and 7. Baseline HAI levels will be included in these models as a covariate. Each HAI titer assessed will be used to compare the two treatment groups. In addition, analyses specific to the virus of infection, will be carried out. For participants infected with H1N1, A/California/2009 and A/Michigan/2015 will be used; for those infected with H3N2, A/Hong Kong/2014, A/Switzerland/2013 and A/Texas/50/2012 will be used; and for those infected with influenza B virus, B/Phuket/2013, B/Brisbane/2008 and B/Massachusetts/2012 will be used.

I. Safety Endpoints

Targeted symptoms are collected at baseline day 3 and day 7. Unsolicited grade 3 or 4 adverse events are collected on days 1-3, 7, 14, and 28. SAEs are collected throughout the 28 day follow-up. The following will be summarized:

- Percentage of participants for whom infusion was interrupted.
- Percentage of participants with adverse events of grade 3 or 4 severity.
- Percentage of participants with a serious adverse event (SAE).
- Percentage with a composite outcome of death, SAE, infusion interruption, or any grade 3 or 4 adverse event.
- Percentage of participants with each targeted symptom on day 3 and on day 7

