- Change in serum chemistries and complete blood count (CBC) between baseline and day 7.

Analysis Considerations for Safety Outcomes

Adverse events will be compared for the IVIG and placebo groups and summarized using chi-square statistics stratified by geographic region. Serum chemistry and CBC measurements will be summarized as changes from baseline to Day 7 using analysis of covariance stratified by clinical site (local laboratories were used).

J. Baseline Characteristics

Tabulations will be prepared by treatment group for a number of baseline variables:

- Influenza subtype
- Age
- Gender
- Race/ethnicity
- Enrollment ward/use of O₂
- Geographic region
- Northern/Southern hemisphere/Equatorial
- Duration of symptoms prior to randomization
- New score
- Influenza season
- Co-morbidities
- Complications
- Subtype/viral load as defined for subgroups
- Influenza vaccination
- Smoking status
- Use of antiviral medication at time of randomization and of those given antivirals the percentage given oseltamivir.

Summary statistics will include N, mean, SD, median, 25th, 75th percentiles, and percentages for categorical variables. Categorical variables will be defined as for the subgroup analysis.

K. Infusion Summary

The following statistics will be used to summarize the infusion in each treatment group:

- Number and percentage of participants receiving complete infusion, partial infusion, or not infused.
- Among participants infused, the day of infusion (same day as randomization, next day, > 1 day after randomization).
- Among participants infused, time between randomization and beginning of infusion (median minutes, 25th, 75th percentiles).
- Among participants infused, estimated dosage administered (median mL, 25th, 75th percentile).
- Among participants receiving full infusion, duration of infusion (median minutes, 25th, 75th percentiles).
- Number and percentage of participants with a grade 3/4 AE or SAE during the infusion.

- Listing of problems reported during the infusion.

L. Completeness of Follow-up

According to protocol, participants are to be seen for data collection at day 1, 3 and 7 after randomization. In addition, data collection (by telephone or in person) was required at day 2, day 14, and day 28. The completeness of follow-up will be summarized by treatment group with the following statistics for the participants infused:

- Number and percent of participants attending each required visit.

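### SAP section I compares targeted symptoms as crude Day 3 and Day 7 percentages and leaves the collected Day 0 value unused, so a benefit on influenza symptoms could mask new symptoms after infusion

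*SAP*

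**What the plan says.** SAP section I states that "Targeted symptoms are collected at baseline day 3 and day 7". The endpoint listed beneath it is the "Percentage of participants with each targeted symptom on day 3 and on day 7", with no reference to the baseline value. The protocol's Appendix B schedule likewise places "Assessment of targeted symptoms" on Day 0, Day 3 and Day 7.

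On method, Protocol 6.1 says: "Symptoms reported and AEs will be compared for the IVIG and placebo groups and summarized using chi-square statistics". The analysis paragraph in SAP section I does not name targeted symptoms. It covers adverse events ("Adverse events will be compared for the IVIG and placebo groups and summarized using chi-square statistics stratified by geographic region") and laboratory values ("Serum chemistry and CBC measurements will be summarized as changes from baseline to Day 7 using analysis of covariance stratified by clinical site"). Neither document defines a new, worsened or resolved symptom relative to Day 0, and the baseline table in SAP section J does not list targeted symptoms.

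On the clinical overlap, Protocol 2.4.1 says of IVIG: "Common risks include fever, rash, hives, or headache". Protocol 4.2.5 adds: "Some of these risks are similar to symptoms associated with influenza". The same section limits adverse event collection to new grade 3 or 4 events and to existing events that worsen to those grades.

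**The concern.** Everyone enrolled is in hospital with influenza, so many will already have some of these symptoms on Day 0. For a symptom that influenza and IVIG can both produce, a positive record on Day 3 has two possible meanings. It may be influenza that has not yet resolved, where the trial's hypothesis is that IVIG helps. Or it may be a symptom that started after the infusion, where IVIG may do harm. The planned percentage adds the two, and under the trial's own hypothesis they can move in opposite directions.

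The other measures with a baseline value are handled differently. Laboratory safety values are analysed as change from baseline. In SAP section H, viral load and HAI titers carry the baseline value as a covariate. Adverse event collection itself requires a new or worsened event.

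At stake is what the symptom table can support. A near-zero crude difference might be read as equal tolerability when it could be the sum of a benefit and a harm. Because milder adverse events are not collected, this table is the main place where new grade 1-2 symptoms after infusion could appear as a comparison between arms, for whatever symptoms are on the targeted list.

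**Working it through.** The documents state no rate, power or sample size for targeted symptoms, so there is no planned figure to reproduce. The check asks whether cancellation is arithmetically possible at plausible values, and what the Day 0 split would recover.

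**Inputs from the documents.** The analysis set is 308 (SAP section D) and allocation is 1:1 (Protocol 3.5). An even split, which is assumed, gives 308 / 2 = 154 per arm.

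**Assumed inputs.** Let b be the share with the symptom on Day 0 (the same in both arms in expectation, by randomization), π the persistence rate among those with it, and ν the new-onset rate among those without it. Take b = 0.60, π = 0.20 on placebo and 0.14 on IVIG, and ν = 0.05 and 0.15.

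**Crude percentage.** In each arm, p = bπ + (1 − b)ν.
- Placebo: 0.60 × 0.20 + 0.40 × 0.05 = 0.120 + 0.020 = 0.140.
- IVIG: 0.60 × 0.14 + 0.40 × 0.15 = 0.084 + 0.060 = 0.144.
- Difference: 0.60 × (−0.06) + 0.40 × (+0.10) = −0.036 + 0.040 = +0.004.

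In general the two effects cancel when b × (drop in persistence) = (1 − b) × (rise in new onset).

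**Power.** This uses the normal approximation, two-sided 0.05, both tails counted, with the pooled standard error se0 under the null and the unpooled se1 under the alternative.
- Crude, 154 per arm: mean rate 0.142, se0 ≈ se1 ≈ √(2 × 0.142 × 0.858 / 154) = 0.0398. Upper tail: Φ[(0.004 − 1.96 × 0.0398) / 0.0398] = Φ(−1.86) = 0.031. Lower tail: Φ(−2.06) = 0.020. The total is about 0.05, which is the error rate.
- New onset, 0.40 × 154 ≈ 61 per arm, 5% v 15%: se0 = √(2 × 0.10 × 0.90 / 61) = 0.0543 and se1 = √((0.0475 + 0.1275) / 61) = 0.0536. Φ[(0.10 − 1.96 × 0.0543) / 0.0536] = Φ(−0.12), so power is about 0.45.
- Persistence, 0.60 × 154 ≈ 92 per arm, 20% v 14%: power is about 0.19.

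**Sensitivity to b**, with the same π and ν:

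| Symptomatic on Day 0 | Crude, placebo v IVIG | Crude power | New-onset power (n per arm) |
|---|---|---|---|
| 50% | 12.5% v 14.5% | 0.08 | 0.54 (77) |
| 60% | 14.0% v 14.4% | 0.05 | 0.45 (61) |
| 70% | 15.5% v 14.3% | 0.06 | 0.36 (46) |

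**Other assumed rates.** With b = 0.50, persistence 50% v 40% and new onset 5% v 15%, the crude rates are 27.5% v 27.5%, an exact cancellation. With b = 0.80 and the same π and ν, they are 0.80 × 0.50 + 0.20 × 0.05 = 41.0% on placebo and 0.80 × 0.40 + 0.20 × 0.15 = 35.0% on IVIG. The crude table would then favour IVIG by 6 points although new onset had tripled.

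**Would one baseline-adjusted model do instead?** In the main illustration the odds ratio (IVIG to placebo) is (0.14/0.86) / (0.20/0.80) = 0.65 for persistence and (0.15/0.85) / (0.05/0.95) = 3.35 for new onset. A logistic model with the Day 0 symptom as a covariate and one treatment term averages these. It can gain precision, but it does not separate the two effects.

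**The case against.** The strongest reply is that the planned comparison is not biased. With 1:1 randomization, the difference in symptom prevalence on Day 3 or Day 7 is a valid estimate of the net effect. The protocol saw the overlap and chose to compare arms irrespective of perceived cause, which avoids biased attribution. This stands. The point concerns what a net difference can be taken to mean.

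Second, the list of targeted symptoms is not in the documents. Cancellation needs a symptom that is targeted, common at entry and caused by IVIG. Fever or headache would fit if listed. The documents do not describe rash and hives as influenza symptoms. If those are listed and rare on Day 0, the crude percentage is already close to new onset. If they are not listed, no split can show them. This also stands, and it limits the point to shared symptoms.

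Third, other measures partly cover harm: infusion interruption, grade 3 or 4 events, SAEs and their composite (SAP section I), and the listing of infusion problems (SAP section K), which has no stated grade limit. What remains uncovered is mainly grade 1-2 symptoms that begin after the infusion.

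Fourth, the split is modest in power and not a pure measure of harm. New onset can include influenza progression, and it omits IVIG reactions in people who already had the symptom. A reaction gone by Day 3 is missed either way.

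A reader might infer that the plan will hide IVIG reactions, or that this endpoint is really an efficacy measure. The documents do not support either. Offsetting effects are possible but not shown, and every rate above is assumed.

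**Conclusion.** The point holds as a limit on interpretation. The crude Day 3 and Day 7 percentages are valid for net prevalence, but for symptoms shared by influenza and IVIG reactions they cannot tell faster resolution from new onset, and the Day 0 data that would help are collected and left unused. In the main illustration, a tripling of new onset (5% to 15%) leaves a crude difference of 0.4 percentage points with power equal to the error rate, against about 0.45 once split. Even split, such a harm would be missed slightly more often than found.

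This rests on assumed rates, an even division of the 308 participants, and at least one targeted symptom being of the shared kind. That each symptom is scored as present or absent is inferred from the word percentage, since no symptom grading is described. The primary analysis and its conclusion are unaffected. This is a cheap improvement to a descriptive safety table and worth making.

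**What to change.** In SAP section I, keep the crude percentage for each targeted symptom on Days 3 and 7 and add two rows by treatment group, stratified by geographic region:

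- **New onset**: participants without the symptom on Day 0 who report it on Day 3 or Day 7, labelled as the tolerability measure.
- **Persistence**: participants with the symptom on Day 0 who still report it, labelled as supportive efficacy.

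Name the method for symptoms in the analysis paragraph, which now omits it, and tabulate Day 0 symptoms by arm in SAP section J. A baseline-adjusted model may be added but should not replace the split.

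The cost is a few sentences and one division of a planned table, with no new assessment. The SAP was written by blinded statisticians, so the rows can be specified before unblinding. The downside is small: smaller denominators, more comparisons, and a new-onset row that can still contain influenza progression. The rows should therefore be presented as descriptive, with counts and denominators shown.

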3.5 Randomization

Eligible patients will be randomized in a 1:1 ratio to receive either IVIG + SOC or placebo + SOC. Randomization will be stratified by clinical site.

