Outcome at Day 3	FLU IVIG Pooled Outcome Data at Day 3 (N=324)	Outcome at Day 3	FLU IVIG Pooled Outcome Data at Day 3 (N=323)
Death	0.3	Death	0.3
ICU	6.5	ICU	6.5
Non-ICU hospitalization, NEW score ≥ 3	17.3	Non-ICU hospitalization, on O ₂	21.4
Non-ICU hospitalization, New score < 3	34.0	Non-ICU hospitalization, not on O ₂	30.0
Discharged	42.0	Discharged, not back to normal activities	34.7
Not applicable (NA)	NA	Discharged, back to normal activities	7.1

In summary, with both the 5-category and 6-category day 3 ordinal outcomes, the odds ratio which can be detected with power=0.80 is approximately 1.77 (assuming 324 participants and a 2-sided type 1 error of 0.05). This is very similar to the odds ratio specified in the design (1.77) for day 7. Even if the proportional odds assumption is violated, power is expected to be similar to 0.80 if the overall assumed odds ratio is maintained. However, considering the category percentages in Tables 2 for day 7 and in Table 5 for day 3, the significance of the final result is likely to be more heavily influenced by differences in the non-ICU hospitalization and discharge (overall or not back to normal) categories at day 3 and by the differences in the two discharge categories (not back to normal and back to normal) at day 7.⁹

Analysis Considerations for the Key Secondary Outcomes

The analysis of the day 3 ordinal outcomes will follow the same plan as for the primary ordinal outcome at day 7. Logistic regression will be used to summarize the difference between the IVIG and placebo group in the favorable outcome at day 7. This model will be stratified by geographic region and include indicators for the participant's clinical status at entry (ICU, general ward on supplemental oxygen, general ward not on supplemental oxygen), and an indicator for whether the participant was in the IVIG pilot trial (FLU 005) or the FLU-IVIG trial (FLU 006).

For participants in the IVIG Pilot, the NEW score was not collected. It will be estimated using the reported vital signs each day. Level of consciousness was not collected. It will be assumed to be zero, therefore NEW scores for these participants may be underestimated. For participants in FLU-IVIG (FLU 006), NEW scores were to be collected twice daily through day 3 while hospitalized. Thus, the NEW score on day 3

will use the average of 2 readings if available, otherwise the single reading collected will be used.

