If a NEW score is not available on Day 3, the last available follow-up NEW score will be used.

For the favorable outcome on Day 7, for the 4 participants who are missing the primary outcome on Day 7, it is presumed that they did not die or were re-hospitalized following discharge, i.e., they will be considered as having a favorable outcome.

H. Supportive Efficacy Endpoints

The following efficacy outcomes are defined as supportive:

- Time to discharge
- Time to death
- Percentage alive and out of the hospital at day 28
- Change in nasopharyngeal viral load from baseline to day 3
- Change in HAI titers from baseline to day 1, 3 and 7
- Percentage dying or requiring re-hospitalization after discharge
- Percentage with a diagnosis on or after the day of randomization and before the day 28 visit developing acute respiratory distress syndrome, acute renal failure, sepsis, pneumonia, enteritis or bronchitis (considered individually and also any of the diagnoses)
- Ordinal outcome on day 14
- Percentage alive and out of the hospital at day 14
- Resumption of normal activities at day 14.
- Ordinal outcome on day 28

Analysis Considerations for Supportive Efficacy Outcomes

Kaplan-Meier curves will be used to summarize the time to discharge and time to death, overall and through 7 days. The median number of days from randomization to discharge will be estimated. Deaths during hospitalization will be censored after day 28 (or day 7) for analyses of time to discharge. A logrank test will be used to compare treatment groups.

For participants who experienced multiple hospitalizations during follow-up, the time to the last discharge before day 28 will be considered. As the visit window for the day 28 visit extends to day 35, events after day 28 but prior to the final visit will be included in these analyses.

The difference between the IVIG and placebo group for change in log-transformed nasopharyngeal viral load from baseline to day 3 will be summarized using stratified analysis of variance with baseline viral load as a covariate. Viral loads vary by subtype. Therefore, strata will be defined by influenza virus subtype (H1N1, H3N2, or B) as well as geographic region. In these analyses, levels below 75 copies, the lower limit of detection, will be imputed as 75 copies. For this analysis, deaths (currently one

participant) on or before day 3 will be excluded, as will participants with undetectable RNA.

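### Adverse events are tested by region only; adding entry clinical state to the pooled safety comparisons would be a cheap gain, though the planned test is valid

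*SAP*

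**What the plan says.** - **Safety test.** SAP I, Analysis Considerations for Safety Outcomes: "Adverse events will be compared for the IVIG and placebo groups and summarized using chi-square statistics stratified by geographic region". Protocol 6.1 named no strata: "Symptoms reported and AEs will be compared for the IVIG and placebo groups and summarized using chi-square statistics". The SAP has therefore already refined the protocol by adding region. Neither document mentions an odds ratio, risk difference or confidence interval for adverse events.
- **Binary efficacy outcomes.** SAP H: "Binary outcomes will be summarized with logistic models that are stratified by geographic region and include indicators for the participant's clinical status at entry", together with an indicator for pilot or main trial. SAP G treats the favorable day 7 outcome in the same way: "This model will be stratified by geographic region and include indicators for the participant's clinical status at entry".
- **Efficacy analyses without entry state.** Undetectable viral RNA at day 3 uses "logistic regression with baseline viral load as a covariate and geographic region and influenza subtype as stratifying factors". For time to discharge and time to death, "A logrank test will be used to compare treatment groups".
- **Allocation.** Protocol 3.5: "Randomization will be stratified by clinical site". Entry state is not a stratum.
- **Baseline table.** SAP J tabulates enrollment ward and oxygen use by arm, so an imbalance would be seen.

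**The concern.** Any grade 3 or 4 event, any SAE and the safety composite are yes/no outcomes. Their risk plausibly depends on whether the patient entered from the ICU, the ward on oxygen or the ward without it. The SAP treats that state as worth adjusting for in its primary model and in most binary efficacy outcomes, but not here, and it gives no reason.

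One consequence is that the same clinical event can be analyzed in two ways. Acute renal failure, sepsis, pneumonia and acute respiratory distress syndrome are supportive efficacy outcomes in SAP H and are adjusted for entry state. When such an event is also grade 3 or 4, or an SAE, it enters the safety comparison by region alone. Renal failure is a named IVIG risk in Protocol 2.4.1 and 4.2.5.

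Two things are at stake: some power to detect harm, and how the result reads if the arms happen to differ in ICU patients. Adjusting only after the baseline table has been seen would be post hoc.

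**Working it through.** **Stated figures.** The documents give no power, event rate or sample size for any safety endpoint. The nearest stated figure is the primary-endpoint sample size. By the method that the protocol cites for ordered categories, N = 12(z_α + z_β)² / [ln(OR)² (1 − Σp̄³)]. With z values 1.960 and 0.842, OR 1.77 and the average design percentages (SAP Table 2), Σp̄³ ≈ 0.095 and N = 12 × 7.849 / (0.326 × 0.905) ≈ 319, against the planned 320. It reproduces, but says nothing about safety.

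**Inputs from the documents.** Analysis set 308 (SAP D), 1:1 allocation (Protocol 3.5), so 154 per arm.

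**Assumed inputs.** Three regions with shares 45/30/25%; ICU share at entry 5, 10 or 20%; oxygen share 35%; event rate 10 or 20% on the ward off oxygen; ICU odds ratio 3, 6 or 10 and oxygen odds ratio 1.5, both against that group; true treatment odds ratio 2 (or 1 for the null).

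**Power.** 5,000 simulated trials per setting compared a Cochran-Mantel-Haenszel test stratified by region with one stratified by region × entry state (9 strata). Each ICU odds ratio covers six settings.

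| ICU odds ratio | Change in power (points) | Example, region only → with entry state |
|---|---|---|
| 3 | −0.7 to +0.2 | 0.774 → 0.774 (10% ICU, 20% rate) |
| 6 | +0.5 to +3.1 | 0.760 → 0.782 (10% ICU, 20% rate) |
| 10 | +1.6 to +7.8 | 0.570 → 0.648 (20% ICU, 10% rate) |

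Type 1 error was 0.046–0.055 by region and 0.044–0.054 with entry state added.

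Two further scenarios let oxygen matter more. Placebo rates of 50/30/15% (ICU, oxygen, neither) with shares 10/40/50% gave 0.73 → 0.76. Rates of 65/35/12% with shares 12/40/48% gave 0.66 → 0.73.

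**Chance imbalance in ICU share.** 95% range = ±1.96 × √(4p(1 − p)/308). For p = 10%: 1.96 × √(0.36/308) = 1.96 × 3.42 = ±6.7 points. For p = 20% it is ±8.9 points.

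**Effect of an imbalance at that limit.** With a 15% event rate outside the ICU, 10% ICU entry and an ICU odds ratio of 6, the ICU rate is 51.4%. The risk difference then moves by 6.7 × (0.514 − 0.150) = 2.4 points, against a standard error of 4.4 points. Over ICU shares of 6.5–20% and odds ratios of 3–10, the shift is 1.1–4.4 points against standard errors of 4.2–4.9, always below one standard error. (The 6.5% borrows the day 3 ICU figure in SAP Table 5; it is not an entry figure.)

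**Results given such an imbalance.** The two further scenarios were repeated with the ICU difference fixed at its 95% limit (6.7 and 7.3 points).
- Excess in placebo, true odds ratio 2: power 0.58 by region against 0.75 with entry state, and 0.44 against 0.73.
- Excess in IVIG, no true effect: chance of a false harm signal (nominal 0.025) 0.060 against 0.029, and 0.075 against 0.024.

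**The case against.** The strongest reply is that the planned test is sound. Over repeated trials, chance imbalance in ICU patients is noise that the 5% error rate already covers, and this applies to any covariate left out. That stands. A reader might infer that the safety comparison is biased or its p-value unreliable; the simulated error rates do not support this. What remains is narrower: if one arm of this trial does receive clearly more ICU patients, the region-only result is harder to read. The conditional figures above describe the edge of the chance range and are not typical.

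Three further points also stand.
- A reader might infer that nothing balances ICU patients. Randomization balances them in expectation, and site strata help to the extent that ICU enrollment differs by site.
- A reader might infer that safety is tested more weakly than all of efficacy. The logrank tests and the viral RNA analysis also omit entry state.
- Some serious harms, renal failure among them, already receive an adjusted analysis in SAP H, and the DSMB reviews safety every 6 months.

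A practical objection is that a model with region, entry-state and pilot terms (only 16 pilot participants) may fail for rare events. It does not count against adding strata for common pooled endpoints, which needs no model to converge.

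**Conclusion.** A minor, optional improvement. SAP I leaves out a baseline factor that the SAP uses in its primary model, its favorable day 7 outcome and most binary supportive outcomes. The region-only test remains valid, and nothing here contradicts the protocol.

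For a harm odds ratio of 2 with 308 participants, the change in power is about 0 to 8 points: none at an ICU odds ratio of 3, up to about 3 points at 6, and close to 8 only when ICU entry is both common (20%) and very strongly prognostic (odds ratio 10). Event rates, entry shares and prognostic strength are all assumed. It is tempting to turn the gain into an equivalent number of extra participants, but the documents cannot fix such a figure and its range would include zero. The further benefit is protection, decided in advance, against an ICU imbalance in the trial as run.

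**What to change.** In SAP I, before unblinding, take three pooled endpoints (any grade 3 or 4 adverse event, any SAE, and the composite of death, SAE, infusion interruption or grade 3 or 4 event). For these, either add entry state to the chi-square strata or prespecify the logistic model of SAP H. Name one of the two, and report the odds ratio with a 95% confidence interval. Keep the region-stratified chi-square for individual event types and for sparse events such as infusion interruption.

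The cost is about one sentence in the SAP and a little more analysis; the data are already collected and the model is already in the plan. The drawback is that the fallback for sparse events must be fixed in advance, by naming the endpoints or stating a minimum event count, so that the test is not chosen after the counts by arm are known. If entry state proves weakly prognostic, the extra strata cost almost nothing (at most 0.7 points of power in the settings above).
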